# 4.3.2 Treatment protocol

Both interventions will be delivered by trained rheumatology health care professionals, such as rheumatology nurses, occupational therapists and physiotherapists, with a preexisting understanding of IRDs. Participants will be offered seven one-to-one telephone or internet-based audio/video call (based on patient preference) sessions (up to 45 minutes) of CBA or PEP interventions with a trained rheumatology health care professional. The first session of the PEP intervention, however, will be delivered faceto-face. PEP may be delivered by a rheumatology specialist physiotherapist and CBA may be delivered by a rheumatology nurse or alternatively an equally qualified and trained allied health professional. A booster session will be conducted at 22 weeks after start of therapy by the relevant rheumatology health care professionals.

# 4.3.3 Training of therapists before the study

Separate CBA and PEP training will be provided for the rheumatology nurses and physiotherapists. This will comprise an intensive 3-day group course delivered by experienced designated investigators (see delegation log in Trail Management File, TMF) supplemented with the modified therapist manuals. The course will utilise a range of methods including skills practice with specific feedback using fictitious but typical fatigued cases.

# 4.3.4 Supervision and support of therapists during the study

Supervision will be provided by designated investigators (see delegation log in TMF) on a fortnightly basis, as required, to the rheumatology health care professionals either face to face or by telephone depending on feasibility and preference. Some of the sessions will be recorded and used in supervision to provide feedback to rheumatology health care professionals and to ensure treatment fidelity. We aim to take a 5% sample of sessions from individuals who agree to be recorded which is based on a random sample generated from an algorithm that takes into account session number, therapist, site location, patient gender. 5% of total number of sessions for those in CBA and PEP is 89 recordings, however this will be subject to participant agreeing to be recorded and treatment adherence (no sessions completed).

In addition, support will be available in cases where a rheumatology health care professional requires assistance with respect to a particular participant. In addition to direct contact option with the supervisor, we will have a notification system incorporated in the database provided and maintained by CHaRT (see 8.2). After secure log-in, the rheumatology health care professional is able to log a report with details about the issue using the participant ID number but no further identifying details included. The database will, if requested, notify the designated investigator or nominated deputy if unavailable as summarised in the delegation log in the TMF, who will provide clinical input if necessary or identify either designated supervisor to provide support if an intervention

specific issue is raised. We will aim to arrange for the rheumatology health care professional to be contacted within 24 h (based on normal working hours) regarding the issue and agreement reached on the required action to be taken and by whom.

# 5 STUDY POPULATION

## 5.1 Number of Participants

Based on the sample size calculation (see 10.1), 100 evaluable participants per treatment are required. The data of participants are evaluable when outcomes at the 56 weeks follow-up are available. Based on our own previous studies, we estimate a dropout rate of 20% and therefore we anticipate recruiting 125 participants in each treatment group, or 375 participants previously diagnosed with IRD (e.g. RA, SLE and AxSpA, psoriatic arthritis, vasculitis or Sjogren's Syndrome).

# 5.2 Participant Selection and Enrolment

Local procedures at the participating study sites are different and the recruitment process may vary in order to accommodate the specific circumstances at each site. Study posters and leaflets will be available at NHS premises of study sites and displayed on websites and social media to increase awareness of the study. Patients are asked to contact their Rheumatology team if they are interested in the study as enrolment is by invitation only. All potential participants will undergo a two-step screening process consisting on a pre-study invite and an assessment of their medical notes to identify potentially eligible participants. All participants will provide written informed consent before they undergo the baseline assessment visit and randomisation to one of the three intervention groups (see 4.3.1).

# 5.2.1 Identifying Participants

A nurse who is a member of the direct care team will identify potential participants using established databases and/or by searching of clinic lists at each study site. Patients with rheumatologist diagnosed IRDs (e.g. RA, SLE and AxSpA, psoriatic arthritis, vasculitis or Sjogren's Syndrome) will be selected. Each potential participant will be contacted by the direct care team on behalf of the local Principal Investigator first. They will receive a pre-study invite either by post or at the time of a rheumatology appointment consisting of a cover letter (see Appendix 1 for details on SWAT Study within a Trial), study information and a few questions to explore interest and eligibility. They will also be asked to give permission for the local research personnel to access their hospital medical notes to further screen for eligibility and for permission to be contacted by the study team (local and central).

If a participant has been identified as potentially eligible a member of the local research team will contact the potential participant within a week to invite him/her to an appointment for a baseline assessment visit at the local study site.

# 5.2.2 Screening for Eligibility

After return of the pre-study invite, the research personnel at each study site will assess their medical notes to determine eligibility based on the inclusion and exclusion criteria summarised in 5.2.3 and 5.2.4. A trained rheumatology research nurse will review and confirm eligibility. In addition, the local rheumatology consultant will have the opportunity to withdraw (see 6.3) or exclude participants.

# 5.2.3 Inclusion Criteria

In order to be considered eligible for participation in the study they must:

- be ≥ 18 years at the time of consent
- have been diagnosed by a rheumatologist with an IRD such as RA, SLE or AxSpA
- report fatigue to be a persistent problem as evidenced by answering both questions:
  - Have you had problems with fatigue for more than three months? (Yes)
  - Please circle the number that shows your average level of fatigue during the past 7 days. (≥ 6 based on a scale of 0 (no fatigue) to 10 (totally exhausted))
- have access to a telephone landline or mobile telephone and/or internet based audio/video calls
- give permission for researchers to access their hospital medical notes
- currently be under the care of a secondary care physician
- have stable disease as evidenced by no change in immunomodulatory therapy within the last three months based on the hospital medical record

# 5.2.4 Exclusion Criteria

Participants will be excluded if:

- there are significant abnormalities of thyroid function (TSH levels) on the most recent blood test done within the last three months
- there is evidence of severe anaemia (haemoglobin levels) on the most recent blood test done within the last three months
- there is evidence of severe renal dysfunction (eGFR) on the most recent blood test done within the last three months
- they have a medical condition which would make the proposed interventions unsuitable, e.g. significant heart disease
- they are pregnant
- they are unable to understand English sufficiently to take part in the intervention
- they are unable to provide written informed consent
- they are not willing to be randomised
- they are currently participating in an interventional clinical trial

# 5.3 Consenting Participants

The potential volunteers will make a decision to participate when they attend the local study site for the baseline assessment visit. An appropriately trained member of the research personnel at each site will obtain informed written consent from the participants.

During the first baseline assessment visit, a designated member of the local research team will determine interest in participating and confirm potential eligibility (including reconfirmation of fatigue state). He/she will explain the study and answer any questions, which the patient has but will also raise issues of feasibility of use of telephone and, if necessary, investigate whether they have for example a hands-free option on their telephone. If a suitable option is not available, a telephone with hands-free function (owned and maintained by the LIFT study team) will be loaned for the intervention period.

No study specific procedures will take place before written consent has been obtained. Once the participant is ready to provide informed written consent, the patient will complete the baseline assessment forms, have clinical information recorded and will be screened for other treatable causes of fatigue. Therefore, the research nurse will take a blood sample to measure thyroid function, haemoglobin and renal function, if these have not been assessed within past three months. Should the person become ineligible as result of the blood test, we will follow the procedure for ineligible participants. In addition, a blood sample is taken to measure CRP and ESR as well as blood samples (1 x PAXgene RNA, 1 x PAXgene DNA, 1 x serum) for storage for future ethically approved research. Procedures for reporting all study blood results will be in place (see also 9).

Participation in the LIFT study will be recorded by the nurse in the hospital medical records together with a copy of the signed consent form.

The research nurse will also determine whether the participant has ever met the relevant classification criteria for RA (mandatory), or other IRDs (non-mandatory):

1) RA (2010 American College of Rheumatology/European League Against Rheumatism RA criteria [50] or 1987 American College of Rheumatology RA criteria [51]),

2) SLE (1997 American College of Rheumatology SLE criteria [52]) and

3) AxSpA, (Assessment of Spondyloarthritis (ASAS) criteria for AxSpA [53]).

#### 5.4 Procedure for ineligible and non-recruited participants

The research nurse or other member of the research team will complete the relevant section of the case report form (CRF) for each person and the reasons for ineligibility will be recorded. If the reason for ineligibility is reversible with appropriate treatment, e.g. change in immunomodulatory therapy, thyroid disorder or anaemia, the potential participant may be contacted at a later stage and, if appropriate, re-invited for assessment including re-consenting and new participant ID. Patients who selected 5 for their average level of fatigue may be re-sent an invitation after 3 months, if appropriate. The collected anonymised data will be stored in the designated database for evaluation but no further data will be collected from the participant unless the person specifically requests to destroy all collected, questionnaires and data during the formal withdrawal procedure (see 6.3).

# 6 RANDOMISATION AND BLINDING

## 6.1 Randomisation Details

After the patient has provided written consent to participate in the study and eligibility has been confirmed, the member of the local research team will randomise the participant via the Clinical Trials Unit (CTU). The CTU is the Centre for Healthcare Randomised Trials (CHaRT) based within the University of Aberdeen. The CTU provides a 24 h randomisation web based service. Using a computer generated sequence, participants will be allocated to receive either of the two treatments or usual care (1:1:1 ratio). Randomisation will be minimised by diagnosis (RA, SLE, AxSpA or other IRD) and the presence/absence of depressive symptoms (Hospital Anxiety & Depression Scale (HADS) depression subscale >10) and will include a random element set at 20%. That is, 20% of all the allocated randomisations will be randomly re-allocated 50:50 to the remaining two treatment options.

Randomised participants will be contacted by the study co-ordinator (or designated deputy if unavailable) by post, email and/or telephone with information about their intervention and details of their allocated therapist, if applicable. All personal contact details will be only accessible in the password protected study database (see 8.2).

# 6.2 Blinding

Full blinding will not be possible due to the need to engage people in behavioural change. However, to reduce detection bias, we will aim to blind research personnel undertaking outcome assessments to participants' treatment allocation. To facilitate blinding we will remind participants to refrain from discussing (and subsequently revealing) their treatment allocation at follow-up assessments with the research personnel. Finally, data will be analysed blind to allocation.

# 6.3 Withdrawal Procedures

Participants will have the option to withdraw at any time during the study period of 13 months. The participant needs to request this formally and a withdrawal document will be completed and signed by the designated research staff at the local sites. They have the option to either withdraw from the study completely or from parts of it (pre-study invite, treatment or follow-up). If participants withdraw from the study completely or from follow-up assessments, they will not receive further invitations but we will use the data collected prior to the withdrawal (depending on permission). Those withdrawing from the treatment only will continue to be sent invitations to attend and complete follow-up assessment visits, unless they request to withdraw completely later on. Failure of any participant to complete a follow-up at any particular time-point will not be counted as a withdrawal unless the participant formally requests to withdraw. In addition, a participant can also be withdrawn by others, for example the local PI or primary consultant, should the need arise at any stage throughout the study period. This also includes loss of capacity for continuous consent.

# 7 STUDY AND SAFETY ASSESSMENTS

There are unlikely to be major safety issues with our proposed non-pharmacological interventions. However, if the rheumatology healthcare professional delivering CBA and PEP or any study personnel have any safety concerns, we will follow a specific Standard Operating Procedure (SOP) for adverse events in non-CTIMP studies. In brief, they will use a standard template after secure log-in into the study database. A designated investigator with rheumatology background and/or designated experienced investigators responsible for the training of therapists as summarised in the delegation log in the TMF will then assess and categorise events according to the SOP to determine if the event is expected, related and/or serious. There will be access to independent clinicians (both rheumatology and psychology), if required. We will make every effort to report all confirmed related serious adverse events to the sponsor within 24 working hours after the CI has been made aware of them.

# 8 DATA COLLECTION AND MANAGEMENT

# 8.1 Data Collection

Case Report Forms (CRF), including medical outcomes, and guestionnaires as indicated under 3 and 3.8, respectively, are completed during the assessment visits at the local study site either on paper or online in the database. All participants will have the option to complete the questionnaires and diaries online in the database (requires a valid email address) or on paper depending on personal preference. There will be the option to complete the questionnaire at home, if the participant requests this. Paper questionnaires will then be returned via pre-paid envelopes to the study centre. If the participant opted for online entry, he/she will receive secure access limited to own data in the database via a link sent to a provided email address and/or log-in code. Paper health economic diaries which are filled by the participant throughout the study will also be returned either in person to the local study site or by pre-paid envelope to the study centre Aberdeen. If a participant is entirely unable (e.g. due to mobility issues) to attend a follow-up visit at 10, 28 or 56 weeks in person, but is still happy to continue with the follow-up, the data collection (except blood samples, step test, DAS28) will be done by phone and post. The option for remote data collection will only be used in selected cases at the discretion of the PI/CI/Co-CI if an assessment visit at the local site would be delayed for at least 3 weeks. In case of a participant unable to attend a follow-up visit, the paper questionnaire, diaries and ActivPAL will be sent out by post and will be returned via pre-paid envelopes to either the study centre or the local study site. In case of a local site unable to perform a follow-up visit, the Trial Office staff will perform the remote visit instead. Information from medical records will be taken retrospectively once the local site is in a position again to continue. Any participants who do not return a questionnaire at the 56 weeks follow-up visit will be telephoned and asked some questions over the phone about fatigue (i.e. Chalder Fatigue Scale, Fatigue Severity Scale), Patient Global Impression of Change, Disease activity and intensity of pain. Personal data, including postal address, phone numbers (landline and mobile), email addresses, and anonymised data files for study outcomes are stored in locked filing cabinets (hard copy) and in a bespoke database provided and maintained by CHaRT (see 8.2) as well as secured shared drives with access via password controlled computers (university and NHS networks) by study staff only (electronic data) (see also 13.1.1 and 13.1.2). Participants will have the option to undertake a multi-modal MRI brain scan (see Appendix 2). A subgroup of participants and all therapists will have the option to take part in an interview as part of the Qualitative Evaluation sub-study (see Appendix 3).

# 8.2 Data Management System

A study specific database will be established and maintained by CHaRT. The access to the database is password controlled with personal access rights (see also 13.1.1 and 13.1.2). The structure and content of the database will be individualised based on the protocol, the study outcome questionnaires and CRF. Individual requirements such as screening log and report functions for continuous monitoring of recruitment, randomisation and follow-up will also be incorporated. There will be a read-only role which allows access to the system for audit and monitoring.

# 8.3 Transfer of Data

Personal data including signed consent forms (original hard copy) will be held at to local study site for the duration of the study before they are transferred by tracked surface mail service to the study centre/study team in Aberdeen for archiving or destroyed. Copies of signed consent forms and anonymised study outcomes (hard copy) will be transferred to the study centre/study team in Aberdeen by tracked surface mail service for monitoring purposes and data input, respectively. All electronic data is password protected and accessible via the secure database by the study staff from each study site as described in 8.2.

# 9 LABS AND SAMPLE ANALYSIS

This multi-centre study involves a number of standard blood investigations, i.e. TSH, haemoglobin, serum creatinine, CRP and ESR, routinely processed by local NHS laboratories. Blood samples for CRP and ESR analysis and sample storage for future ethically approved research will be taken at each assessment as specified in the study matrix by trained personnel only following established procedures. Blood samples for TSH, haemoglobin and serum creatinine analysis will only be taken at baseline to confirm eligibility, if required. Sample coding, preparation, storage, analysis and transfer of results and optional blood samples for long-term storage at the trial centre will be performed according to the analytical protocol based on national laboratory guidelines. The exact logistic and procedure will be agreed on with each site before the start of the study and we will make every effort to standardise the workflow across sites to reduce bias. Additional optional blood samples will be stored for future ethically approved research). All study blood results (abnormal or otherwise) will also be directed towards the local PI who can determine locally how these will be handled.

# **10 STATISTICS AND DATA ANALYSIS**

#### **10.1 Sample Size Calculation**

Our planned primary intention to treat analyses will compare PEP + usual care versus usual care alone, and CBA + usual care versus usual care alone separately. We base our calculations on a standardised effect size of 0.50 (considered credible in other pragmatic effectiveness studies), which would equate to being powered to detect a minimal important clinical difference of 2 units in the CF Scale, assuming a common standard deviation across the randomised groups of 4 units. Assuming an overall significance level of 5% (by calculating the two pre-specified randomised groups comparisons, PEP + usual care vs. usual care alone and CBA + usual care vs usual care alone, at 2.5%, to maintain an overall level of not more than 5%) and a power of 90%, we require 100 evaluable participants in each of the three groups.

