# 3.1 **Primary Outcome**

The primary outcome fatigue is determined with the Chalder Fatigue Scale (CF) [31] using the Likert scoring, assessing the physical and mental symptoms of fatigue, and the Fatigue Severity Scale (FSS) [32] assessing the impact of fatigue after 56 weeks. If the effect of intervention is positive on the CF, then the FSS outcome will be formally analysed. Should the intervention have no effect on the CF, then an explorative analysis of the FSS outcome will be performed (details see 10.2).

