11.1 General Methods

All the main analyses will be based on the ITT principle and utilise all available follow-up data from all randomised participants who provide consent. Any post-randomisation exclusions will be removed. Final analysis will take place after full recruitment and follow-up. The results of the trial will follow the guidelines of the CONSORT statement developed specifically for social and psychological intervention trials ³ when presenting and analysing the data. Baseline characteristics of the study population will be summarised separately using the appropriate descriptive statistics and graphical summaries within each randomised group. Baseline characteristics will also be presented for dropouts and completers within each intervention group.

Treatment effects will be tested at the 2-sided 5% significance level with any estimates displayed with 95% confidence intervals (CIs) and p-values. There will be no

SAP version 1: LIFT

adjustment to secondary outcomes CIs for multiple testing. (See section 3 for statistician blinding)

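### The fixed 2.5% per therapy is valid, but it is not passed on once one therapy succeeds on both CF and FSS, which costs the other therapy some power within the plan's own 5% cap

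*Protocol*

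**What the plan says.** Protocol 10.1 sizes the trial on a "standardised effect size of 0.50", that is, a "minimal important clinical difference of 2 units in the CF Scale" with a "common standard deviation across the randomised groups of 4 units". Each of the two comparisons with usual care is set "at 2.5%, to maintain an overall level of not more than 5%) and a power of 90%, we require 100 evaluable participants" per arm. SAP 10 repeats this.

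Protocol 3.1 adds a second primary scale in sequence: "If the effect of intervention is positive on the CF, then the FSS outcome will be formally analysed". If CF shows no effect, FSS is only explored. SAP 6.1 says the same. Neither gives the significance level for FSS, and neither contains a rule for passing a level from one therapy to the other.

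SAP 11.1 states a different level for the analysis: "Treatment effects will be tested at the 2-sided 5% significance level", with 95% confidence intervals. It disclaims multiplicity adjustment only for secondary outcomes. The results tables in SAP 13.4 and 13.5 also have 95% interval columns.

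**The concern.** The primary objective puts two questions, one for CBA and one for PEP, and each has two primary scales tested in order. Under an equal split each therapy has its own 2.5%. If one therapy is significant on CF and then on FSS, it has no formal primary test left. Its 2.5% then does nothing more, while the other therapy is still held to 2.5%.

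The protocol's own ceiling is 5% overall. In that situation the plan runs below the ceiling, and the second therapy is more likely to be declared unproven than the ceiling requires. What is at stake is modest: some power for the second therapy's CF and FSS claims, at no cost in patients or data.

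**Working it through.** **Inputs.** From Protocol 10.1: difference 2, SD 4, 2.5% per comparison, 90% power, 100 evaluable per group. From Protocol 6.1: "participants will be allocated to receive either of the two treatments or usual care (1:1:1 ratio"), so the two comparisons share a control group and their test statistics correlate at 0.5. Assumed, because the documents are silent: FSS is tested at its therapy's own level, the CF-then-FSS order applies to each therapy separately, the CF-FSS correlation is 0 to 0.8, and the true FSS effect is as shown below. All figures use the normal approximation and the unadjusted SD of 4.

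**1. The plan's own figure.** n = 2(z₀.₉₈₇₅ + z₀.₉₀)² / 0.5² = 2(2.2414 + 1.2816)² / 0.25 = 99.3, so 100 per group, as stated. The match requires a two-sided 2.5% test; a two-sided 5% test, or a one-sided 2.5% test, would need 85. Power at 100 is Φ(0.5/√0.02 − 2.2414) = Φ(3.5355 − 2.2414) = 90.2% (89.8% with the t distribution).

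**2. What a 5% level is worth.** At 5%, power for one comparison is Φ(3.5355 − 1.9600) = 94.2%. Under the fixed split, with both true CF effects at 0.5 SD, simulation gives 83.6% for both therapies and 96.9% for at least one.

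**3. Passing the level on after CF alone is not allowed.** Suppose one therapy works on CF only and the other on nothing. The first therapy's FSS test at 2.5% can still give a false positive. If CF and FSS are uncorrelated and the CF effect is large, the fixed split gives 1 − 0.975² = 4.9%. If the other therapy's CF is tested at 5% as soon as the first therapy's CF succeeds, the error becomes 1 − 0.975 × 0.95 = 7.4%. Over correlations of 0 to 0.7 and CF effects of 0.5 or 1.0 SD, simulation gives 4.0-4.9% for the fixed split and 5.9-7.4% for passing on after CF alone.

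**4. Passing it on after CF and FSS both succeed holds 5%.** There are two cases.
- Each therapy has at least one true null. Neither can complete its CF-FSS sequence without a false positive occurring first, so any first false positive arises at 2.5%. The total is at most 2.5% + 2.5% = 5%.
- One therapy truly works on both scales. False positives can then come only from the other therapy, whose tests run in order at no more than 5%.

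Simulation agrees: the family-wise error is at most 5.0%, within simulation noise, in every null pattern tried.

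**5. Gain at 100 per group, true CF effects 0.5 SD for both therapies.**

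| True FSS effect (both therapies) | CF power per therapy, fixed | CF power per therapy, with the rule |
|---|---|---|
| 0.5 SD | 90.2% | 92.9% |
| 0.3 SD | 90.2% | about 91.4% |
| none | 90.2% | about 90.3% |

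With FSS at 0.5 SD, the chance of showing both therapies on CF rises from 83.6% to 89.0%. For all four claims it rises from 72.6-77.0% to 81.8-84.8% (CF-FSS correlation 0.4 to 0.8). If one therapy's true effect is 0.4 SD, its CF power rises from 72% to 79%. The chance of at least one CF success stays at 96.9%, because both therapies still start at 2.5%.

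**6. What is paid.** If one therapy works on both scales and the other on neither, the family-wise error is 2.5% under the fixed split and 4.3-5.0% under the rule.

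**The case against.** The strongest reply is that nothing is broken. An equal split is a legitimate choice, the trial was sized for it, and the promised 90% per comparison is met. It also lets tests and intervals agree in every case, if intervals are given at 97.5%. All of that stands, and it is why this is an improvement and not an error.

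A second reply is that the loss may not exist. If SAP 11.1 governs and each CF comparison is tested at 5%, power is about 94% each. The problem is then the opposite one: with both therapies null, the overall error is about 9.1%. This also stands. The point applies only once the conflict is settled in favour of the 2.5% split that Protocol 10.1 and SAP 10 describe.

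A third reply is that the size of the gain is uncertain. The documents give no FSS effect, and the gain almost vanishes without one. The planned model also adjusts for baseline. With an assumed baseline correlation of 0.5 and no clustering by therapist, CF power is already Φ(3.5355/√0.75 − 2.2414), about 97%, and the rule takes it to about 98%. Clustering would work the other way.

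A reader might go further and infer that half of the 5% lies idle as soon as one therapy succeeds on CF, or that the extra power costs nothing in error. The documents do not support either reading. Protocol 3.1 and SAP 6.1 send a CF success on to a formal FSS test, so that therapy's 2.5% is still in use until FSS has also succeeded. The extra power is paid for with real error, which stays under the cap.

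**Conclusion.** The point holds as a modest and inexpensive gain in efficiency. The split in Protocol 10.1 and SAP 10 is valid and delivers its stated power, but it leaves a therapy's 2.5% unused after that therapy has succeeded on both CF and FSS. Passing it on then adds up to 2.7 points of CF power per therapy (92.9 − 90.2) and 5.4 points for showing both therapies on CF (89.0 − 83.6).

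These figures rest on 100 evaluable per group, an SD of 4 without baseline adjustment or clustering, true CF effects of 0.5 SD, FSS tested at its therapy's level, and FSS effects as large as the CF effects. They shrink towards zero as the FSS effects shrink. The conflict with SAP 11.1 and the missing FSS level have to be settled whether or not the rule is adopted.

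**What to change.** 1. Reconcile SAP 11.1 with Protocol 10.1 and SAP 10, so that each therapy's CF comparison starts at a two-sided 2.5%.
2. State in Protocol 3.1 and 10.2 and in SAP 6.1 and 11 that FSS is tested at its therapy's current level, and only after CF is significant for that therapy.
3. Add to Protocol 10.1/10.2 and SAP 10/11: *If CF and then FSS are both significant at 2.5% for one therapy, its 2.5% passes to the other therapy, whose CF and then FSS are tested at 5%; otherwise they are tested at 2.5%.* Say explicitly that nothing passes on after CF success alone.
4. Specify the interval level for the primary comparisons in SAP 11.1 and in the primary results table (SAP 13.4). The plan now gives 95%, so 97.5% intervals would be a new choice. If they are chosen, a second therapy significant only at 5% may have an interval that includes zero; explain this in a footnote.

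The cost is wording, the amendment approvals in Protocol 14.1 and renewed approval of the SAP under Protocol 10.2. It needs no extra participants or data. The change must be dated before the outcome data are examined by allocation. The price in error is the rise from 2.5% to at most 5% when one therapy works on both scales.
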